10.2 CONSENT

Describe how and when program applicants will be informed of the study and will have the option of agreeing (i.e., consenting to) or declining to participate in the study.

Because the planned evaluation involves human subjects, Seedco understands program implementation requires both IRB approval and participant informed consent. MER has an established relationship with Solutions IRB having secured more than 20 IRB approvals and renewals for evaluations it has conducts during the past five years. IRB clearance will be submitted for approval and obtained during the planning period.

To secure informed consent participants will attend an orientation / enrollment session (in person) where the Data Manager will describe the evaluation process, the risks and benefits of the project. Those people that wish to participate in the evaluation will complete an informed consent process and sign an informed consent document / form. All participants will receive a copy of the consent form with contact information for evaluation staff and how to contact the IRB if needed. Informed consent will take place prior to program enrollment and the collection of evaluation data.

9.2. METHODS OF DATA COLLECTION

If the evaluation will collect multiple waves of data, describe the timing of these waves below. When describing follow-up periods, specify whether the follow-up period will be post-baseline, post-random assignment, or post-program completion.

Wave of Data Collection	Timing of Data Collection
(e.g., baseline, short-term follow-up, long-term follow-up)	
Pre-Test (Wave 1)	Collected immediately following informed consent and study enrollment – during orientation session or first workshop

	Collected after the completion of core curriculum/primary workshop programing – during the last workshop session – approximately 8 weeks after enrollment/baseline
--	--

For each measure, describe how data will be collected detailing which data collection measures will be collected by which persons, and at what point in the programming or at what follow-up point.

Measure	Timing of Data Collection (baseline, wave of data collection)	Method of Data Collection	Who Is Responsible for Data Collection?	Impact Evaluations Only: Will Methods or Collection Procedures Differ by Study Group?	Administrative Data Only: Will data access require data sharing agreement?
nFORM Entrance Survey	Wave 1	Participant self-enters survey using online data collection platform	Data Manager will proctor data collection and assist participants as necessary		N/A
nFORM Exit Survey	Wave 2	Participant self-enters survey using online data collection platform	Data Manager will proctor data collection and assist participants as necessary		N/A

^{*} you may add rows by hitting the tab button, or right click and select insert row below

9.3. ENSURING AND MONITORING DATA COLLECTION

Describe plans for training data collectors and for updating or retraining data collectors about procedures. Detail plans to regularly review data that have been submitted and to assess and swiftly address problems.

All program staff and evaluation staff will undergo a rigorous set of trainings to prepare for the evaluation. All staff receive an overview and introductory training to present the goals and objectives of the evaluation effort and its importance to the overall project. Next all staff receive training on human subjects protection and are required to pass a certification test on the subject matter. All staff will also receive a detailed training on the details of the descriptive evaluation including the evaluation tools, timing, and data collection processes.

In addition, the Data Manager and the primary local evaluation staff will undergo a rigorous training process to better understand the context of HMRF research, training on data collection procedures they will be responsible for, and training on the nFORM system and use of nFORM data in a CQI process. MER is creating networks of CQI Data Managers and Evaluation Project Managers across the 12 projects that we are evaluating so that all staff have access to experienced data managers and evaluation staff who have done this work previously.

Members of the CQI team will also receive specific training on the MER CQI process that has been developed prior to the launch of data collection or program services. As described elsewhere MER is assisting the program staff in implementing a robust CQI process that will focus on retention as one of the primary areas of program improvement and as such we are anticipating relatively modest levels of attrition for this data collection.

On a bi-weekly basis the local evaluation project lead will be responsible for downloading data from nFORM for processing and presentation to the CQI team for tracking and monitoring performance measurement outcomes (recruitment, enrollment, dosage, completion, referrals, etc.) so that near real time adjustments can be made to program implementation to ensure compliance with program goals and objectives.

As new staff come on board with projects or project staff turnover (or need refresher training), recorded training material can be shared and accessed with follow-up one on one training with the local evaluation project lead and/or the MER Line of Business Lead, as necessary.

10.IRB/PROTECTION OF HUMAN SUBJECTS

Please describe the process for protection of human subjects, and IRB review and approval of the proposed program and evaluation plans. Name the specific IRB to which you expect to apply.

Solutions IRB, a private commercial Association for the Accreditation of Human Research Protection Programs Inc. (AAHRPP) fully accredited Institutional Review Board, will ensure that this study is approved before any research activities take place. MER has had 14 research studies approved by Solutions IRB over the past four years, has completed over 15 annual check-in reports, and has submitted timely amendments when changes to studies needed to take effect.

All submissions are completed online, so turnaround for a new study approval is between 24 to 72 hours, though the full approval process can take approximately one to two weeks depending on the number of questions and requested revisions that the IRB makes. In the IRB

application submission, we will include descriptions of project staff, locations of study sites, the funding source, incentives, summary of activities, participant population, recruitment plans, risks and benefits, confidentiality of data, and the informed consent process along with all materials to be used in the study such as participant forms and surveys.

This revised descriptive study design will be submitted for IRB approval in late July 2023 in order to receive official approval by August 2023.

11.DATA

11.1. DATABASES

For each database used to enter data, please describe the database into which data will be entered (i.e., nFORM and/or other databases), including both performance measure data you plan to use in your local evaluation and any additional local evaluation data. Describe the process for data entry (i.e., who will enter the data into the database).

Database Name	Data Entered	Process for Data Entry
nFORM	Performance Measurement Data	Participant direct entry and staff direct entry (facilitator and case managers)

^{*} you may add rows by hitting the tab button, or right click and select insert row below

11.2. DATA REPORTING AND TRANSFER

For each database provided in the table above, please indicate the ability to export individual-level reports to an Excel or comma-delimited format and whether identifying information is available for linking to data from other sources.

Database Name	Ability to Export Individual Reports?	What identifying information is available to facilitate linking to other data sources?
nFORM	Yes	nFORM client ID

^{*} you may add rows by hitting the tab button, or right click and select insert row below

11.3. CURRENT SECURITY AND CONFIDENTIALITY STANDARDS

For each database provided in Section 11.1, please Indicate the ability to be able to encrypt data access during transit (for example, accessed through an HTTPS connection); be able to encrypt data at rest (that is, when not in transit), have in place a data backup and recovery plan; require all users to have logins and passwords to access the data they are authorized to view; and have current anti- virus software installed to detect and address malware, such as viruses and worms.

Database Name	Ability to encrypt data during transit?	Ability to encrypt at rest?	Data Backup and Recovery Plan?	Require all users to have logins and passwords?	Current Anti- Virus Software Installed?
nFORM	Yes	Yes	Yes	Yes	Yes

^{*} you may add rows by hitting the tab button, or right click and select insert row below

Strong Fathers, Stronger Families Healthy Marriage and Responsible Fatherhood Program Evaluation

Statistical Analysis Plan

Clinicaltrials.gov ID: NCT06907719

8/2/2023

1. Data Analysis

Briefly describe the planned approach for data analysis. If an impact analysis is proposed, name the key dependent and independent variables, and describe any methods to minimize Type I error (i.e., finding positive impacts by chance) such as limiting the number of impacts to be analyzed and/or multiple comparison correction. Describe proposed approach(es) for addressing missing data.

Identify study sample

The study sample includes participants who: 1) gave recorded informed consent to be part of the study, and 2) took both an entrance and exit survey. The CONSORT diagram in Appendix B shows exclusion criteria and the anticipated size of the overall study sample. The analytic sample for particular outcome measures will vary based on missing data.

Defining analysis measures

For each outcome construct, we have identified the relevant measures from nFORM that are theoretically aligned with that construct. We will generate a correlation matrix between items in a given construct to ensure that theoretically related items are also empirically related in our data set. Items that are not strongly correlated with other items in a construct will be removed as necessary. Factor analysis will be used to ensure that all construct items hang together (using an alpha of 0.7 or higher as the threshold).

Once we are confident that all of the items align with a given construct, we will create a composite measure by taking an average of the scores on each non-missing item in the construct. The measure definition matrix below provides information on each proposed outcome. For composite measures, a change score will be calculated between a participant's pre-program composite score and post-program composite score. For standalone survey items, a change score will be calculated between a participant's pre-survey and post-survey responses.

For the sake of consistency and simplicity, parenting and co-parenting analyses will use a participant's youngest child as the focal child.

	Sample		Data	Variable	
Measure		Variable Type	source(s)	Name	Definition
Co-	Has at least one child	Continuous	nFORM	Copar_Beh	Average of five
parenting	age 24 or younger	(range from 1 to 5	entrance,		survey items that
relationship			nFORM		relate to positive
behaviors			exit		interactions with
		and 5 is strongly			the mother of
		agree)			participant's
					youngest child

	saw child within past month	(range from 1 to 5 where 1 is never			Average of 10 to 11 survey items (depending on child age) that relate to frequency of positive interactions with participant's youngest child
•	Has at least one child age 24 or younger, saw child within past month	(range from 1 to 24)	nFORM entrance, nFORM exit		Reported number of hours per day (excluding sleeping) that parent usually spent with their youngest child
Frequency of contact		(range from 1 to 4 where 1 is every	entrance, nFORM exit		Reported frequency of reaching out to youngest child in the past month
Economic stability – checking account	•	(0/1)	nFORM entrance, nFORM exit	_	Binary measure of having opened a checking account by the end of the program
Economic stability – savings account	_	(0/1)	nFORM entrance, nFORM exit	0 _	Binary measure of having opened a savings account by the end of the program
Economic stability – difficulty paying bills		(range from 1 to 4 where 1 is never		_	Reported frequency of difficulty paying bills

Handling missing data

Outcomes

When creating the composite measures for co-parenting and parenting relationships, we will create a composite score by taking the average of multiple individual items. For these measures, our current plan is to use 20% as a threshold for allowable missing items, based on guidance from evaluation technical assistance resources. This plan is contingent on the final distribution of missing data in our data set. With a 20% threshold, if a respondent is missing more than 1 item used for creating the coparenting construct or more than 2 items for creating the parenting construct, the respondent will be assigned a missing value for that construct. We will not be imputing truly missing values for outcomes. To create a construct score, the average will divide by the number of non-missing values in the construct.

Participants who have not seen their child within the past month will have their parenting behavior responses set to "Never" (1) and will be included in the analytic sample for that outcome.

For outcomes that use single survey items, participants who do not respond to the item on either the pre- or post-survey will be excluded from the analytic sample for that outcome.

Missing data for the implementation outcomes could happen as a result of programmatic data entry issues. For the sake of this evaluation, we assume that any primary or support services received by a participant are being accurately logged into nFORM, so a lack of documented attendance, service contacts, referrals, etc. is indicative of lack of services (i.e., a participant not receiving the program components as intended).

...

Assessing non-response bias

We will conduct response rate analysis for each primary outcome of interest to assess non-response bias and adjust for threats to internal validity. Using data from the Applicant Characteristics Survey, we will look at demographics (race, ethnicity, age, education level) and primary reason for joining the program among participants who fall into each of the following categories: 1) non-respondents who answered no surveys after the ACS, 2) respondents who completed the pre-survey only, 3) respondents who completed the post-survey only, and 4) respondents who completed both the pre-and post-survey (complete case).

Analytic approach

The main goal of this descriptive study is to assess pre-post change scores in the outcomes listed above among program participants before and after primary workshops. We will use paired sample t-tests to assess the magnitude and significance of changes among program participants in the analytic sample for each outcome. For binary economic stability outcomes, we will descriptively report the percent of participants who opened a checking or savings account during the course of the

program. We will adjust our p-values for multiple hypothesis testing and report the adjusted p-values in the appendix of the final report.

For the implementation analysis, program fidelity will be descriptively reported by the percentage of enrolled participants who receive: 1) any primary workshops, 2) employment supports, 3) substantive service contacts, 4) referrals. The program aims to provide all participants each of these four program components, so the percentage of participants who receive each of these will be compared to the 100% benchmark. Number of substantive service contacts per participant will also be compared to the benchmark of 8 SSCs set by OFA for FIRE grantees.

Dosage will be measured by percent of target primary workshops participants attend on average (using 90% as a benchmark), and categories of attendance (initial, halfway, 90%, 100%) will be reported and compared to targets established by the program and reported on page 3 above. Exploratory analysis will examine how dosage varies by workshop characteristics (e.g., timing and length of sessions) and participant characteristics (e.g., age, employment status, relationship status)?

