Population: The SFSF-Midsouth Program proposes to serve low-income fathers who face barriers to engagement with their children. These participants will be primarily young fathers, including biological, expectant, and adoptive fathers, stepfathers, and acknowledged father figures. Recruitment will focus on at-risk young fathers, low-income fathers, and active-duty military and veteran fathers living in Shelby County, TN, Tipton County, TN, and Crittenden County, AR. Specific numbers to be served are in the chart below:

PROGRAM PARTICIPATION TARGETS

Milestone	Year 1 4/1/21- 9/29/21	Year 2 9/30/21- 9/29/22	Year 3 9/30/22- 9/29/23	Year 4 9/30/23- 9/29/24	Year 5 9/30/24- 9/29/25	Total
Individuals Screened	225	450	450	450	450	2,025
Participants Enrolled	175	350	350	350	350	1,575
Participants who attend at least one primary workshop	175	350	350	350	350	1,575

Participants who attend at least 50% of primary workshops	165	330	330	330	330	1,485
Participants Graduating Healthy Relationship & Parenting Curricula (attend at least 90% of primary workshops)	158 (90%)	315 (90%)	315 (90%)	315 (90%)	315 (90%)	1,418
Participants who attend 100% of primary workshops	118	236	236	236	236	1062
Participants Placed in Jobs	105(60%)	210 (60%)	210 (60%)	210 (60%)	210 (60%)	945
Job Retention- 30 days	87 (50%)	175 (50%)	175 (50%)	175 (50%)	175 (50%)	787
Job Retention- 60 days	70 (40%)	140 (40%)	140 (40%)	140 (40%)	140 (40%)	630
Job Retention- 90 days	50	100	100	100	100	450
Job Retention- 180 days	40	80	80	80	80	360
Return Post-Graduation for Long-Term Case Management	87	175	175	175	175	787

Memorandum of changes to the Evaluation Study.

- SEEDCO Midsouth will aim to serve the same number of individuals in the descriptive study as in the RCT with a different estimated minimum effect size for the descriptive study. (Evaluation enrollment targets remain unchanged)
- The one-year local evaluation follow-up survey will no longer be collected and has been removed from the evaluation plan.
- The previously administered OLLE pre- and post-surveys will not be administered, as the measures needed to answer R1, R2, and R3 come from nFORM.

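### The non-response check leaves out entrance outcome scores, and ending exit surveys on the last enrolment day puts late enrollees among the apparent dropouts

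*SAP*

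**What the plan says.** **Who is analysed.** Under Identify study sample, the SAP keeps participants who "gave recorded informed consent to be part of the study, and 2) took both an entrance and exit survey". Under Handling missing data it adds: "We will not be imputing truly missing values for outcomes". The tests are paired t-tests on fathers with both measurements.

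**How loss is checked.** Under Assessing non-response bias, the SAP forms four response groups, including "non-respondents who answered no surveys after the ACS", "respondents who completed the pre-survey only" and those with both surveys. The data source is the Applicant Characteristics Survey (ACS), and the variables are stated as: "we will look at demographics (race, ethnicity, age, education level) and primary reason for joining the program". The section says the analysis is done for each primary outcome and is meant to support adjustment. It lists no outcome score and names no adjustment method.

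**When surveys are taken.** Protocol section 9.2 describes the entrance survey as "Collected immediately following informed consent and study enrollment", at orientation or the first workshop. The exit survey is taken in the last workshop session, "approximately 8 weeks after enrollment/baseline". Protocol section 3 (Evaluation Enrollment) ends program and study enrolment on 3/31/2025. Section 4 (Evaluation Timeline) ends pre- and post-survey collection on that same date.

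**The concern.** R1-R3 are confirmatory questions about the fathers the program serves, but they are answered only in those who reach the exit survey. With no imputation, the non-response check is the main stated safeguard against selective loss. A comparison on race, ethnicity, age, education and reason for enrolling can reveal demographic selection. It cannot directly show whether the fathers who were lost began with poorer co-parenting, less contact or more difficulty paying bills. For the entrance-only group, that information is already in the database.

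The dates then weaken whatever comparison is made. A father who enrols in the last 8 weeks has an entrance survey but reaches his final workshop after collection has closed. He leaves the R1-R3 sample because of the calendar and is grouped with fathers who stopped attending. Fathers lost by date should resemble completers, so mixing them in makes a real difference between dropouts and completers look smaller than it is.

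**Working it through.** **Inputs from the Protocol.** Enrolment targets are 175 in Year 1 and 350 in each of Years 2-5. Year 5 runs 9/30/24 to 9/29/25. Enrolment and survey collection end 3/31/2025. The exit survey is about 8 weeks (56 days) after baseline. The targets row "Participants who attend at least one primary workshop" equals enrolment (1,575 of 1,575), so on the plan's own targets nearly every father reaches the point where the entrance survey is given.

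**Plan's total reproduced.** 175 + 4 × 350 = 1,575, as stated.

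**Dates.**
- Last enrolment that allows an exit survey by closing: 3/31/2025 − 56 days = 2/3/2025.
- Closing date that covers the last enrollee: 3/31/2025 + 56 days = 5/26/2025.

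**Fathers lost by date.**
- Even pace through Year 5 (183 of its 365 days fall by 3/31/2025): enrolled = 175 + 3 × 350 + 350 × 183/365 ≈ 1,400. Lost = 350 × 56/365 = 53.7, or 3.8%. Standard error factor = √(1400/1346) = 1.020.
- All Year 5 enrolment completed by 3/31/2025: lost = 350 × 56/183 = 107 of 1,575, or 6.8%. Factor = √(1575/1468) = 1.036.

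**Mixing in the entrance-only group.** The documents give no exit-survey response rate, so let q be the assumed share who stop before the exit survey. With 1,400 enrolled, dropouts = 1400q, and fathers lost only by date = 53.7(1 − q). If the latter have the completers' mean, observed gap = true gap × (1 − date-lost share). For a true entrance gap of 0.25 SD:

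| q | Dropouts | Lost by date only | Date-lost share | Gap seen |
|---|---|---|---|---|
| 5% | 70 | 51.0 | 42% | 0.145 SD |
| 10% | 140 | 48.3 | 26% | 0.186 SD |
| 20% | 280 | 43.0 | 13% | 0.217 SD |

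The 10% row is in line with the Protocol's hypothesis that 90% of enrollees receive at least 90% of primary hours. With 1,575 enrolled and q = 10%, the counts are 157.5 and 107.1 × 0.9 = 96.4. The date-lost share is then 38%, and 0.25 SD appears as 0.155 SD.

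**What an entrance-score comparison could detect** (80% power, two-sided 5%, q = 10%, 1,400 enrolled). Detectable gap = 2.80 × √(1/n1 + 1/n2).
- Dates fixed, every dropout has an entrance score: 140 v 1,260 gives 0.25 SD.
- Half of the dropouts also gave no entrance survey: 70 v 1,260 gives 0.34 SD.
- In addition, the outcome applies to only half of fathers: 35 v 630 gives 0.49 SD.
- Dates not fixed, otherwise best case: 2.80 × √(1/188.3 + 1/1211.7) / (1 − 0.257) = 0.295 SD.

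**Possible effect on the primary result (illustration only).** Shift in completers' mean change ≈ missing share × entrance gap × (1 − pre-post correlation). With an assumed gap of 0.3 SD and correlation of 0.5, this is 0.10 × 0.3 × 0.5 = 0.015 SD at 10% missing and 0.06 SD at 40% missing.

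**The case against.** The strongest reply is that nothing here shows bias in R1-R3. The date loss is administrative and costs 2-4% in standard error, and the illustrative shift in mean change is small at 10% missing. The added comparison is also indirect. Bias depends on how the lost fathers would have changed, and similar entrance scores cannot settle that. With detectable gaps of 0.25-0.49 SD, a null result would reassure only a little. All of this stands, and it limits the weight of the point. It does not make a demographics-only check preferable when entrance scores are in hand.

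A second reply is that the closing date may be only a timeline entry. Exit surveys are part of the program's own nFORM data, the program may go on giving them after March 2025, and the sample definition has no survey-date cutoff. The documents neither state nor exclude this, so the timeline at least needs correcting. The CONSORT diagram in Appendix B is not available here, and an ellipsis stands just before the non-response section, so a rule for late enrollees could exist there. Neither gap alters the variables or dates that the current text does state.

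Third, the mixing figures depend on assumed dropout, and the case in which an outcome applies to half of fathers has no support in the documents. It would not obviously apply to difficulty paying bills, which does not depend on contact with a child. For that reason the results are given as a range.

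**Conclusion.** Both parts hold. As written, the check cannot directly show whether fathers lost before the exit survey differed on the outcomes at entrance. The timeline closes exit-survey collection about 8 weeks too early for the last enrollees.

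The date clash is an avoidable loss of about 4-7% of the sample, not a demonstrated bias. Its larger cost falls on the check: under 5-20% assumed dropout and an even enrolment pace, 13-42% of the entrance-only group would be there because of the calendar. These figures rest on enrolment at target and on date-lost fathers resembling completers. The point should be addressed because both remedies are cheap, but it does not undermine the design.

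**What to change.** 1. **Timeline.** End exit-survey collection at least 8 weeks after the last enrolment, at about 5/26/2025. This costs an edit to the Evaluation Timeline and possibly an IRB amendment. The documents give no analysis deadline; measured against the end of Year 5 (9/29/2025), 126 days would remain. If collection cannot be extended, report fathers enrolled after about 2/3/2025 as a separate group, using enrolment date. That protects the check but does not recover the sample.

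2. **Non-response check.** Keep the ACS comparison across all four groups, since fathers with no entrance survey can be compared only there. Add a comparison of entrance scores between entrance-only and both-survey fathers for co-parenting, parenting behaviours, hours with the child, contact frequency and difficulty paying bills. The two account outcomes have no entrance score to compare, because their samples are fathers without that account at entrance; their results remain open to selection all the same. This is one further comparison from data already collected.

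3. **Use.** State that the result will qualify how far R1-R3 extend beyond both-survey fathers, report the gaps with confidence intervals, and do not read a null result as proof of no selection. If adjustment is still intended, name the method.

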9. DATA COLLECTION

9.1. CONSTRUCTS AND MEASURES

Clearly articulate the constructs of interest, measures to evaluate those constructs, and specific data collection instruments. Provide any information on the reliability and validity of the data collection instruments. For standardized instruments, you may provide the citation for the instrument.

^{*} you may add rows by hitting the tab button, or right click and select insert row below

Construct	Measure	Instrument	Reliability and Validity (if standardized instrument, you provide a citation for the instrument)
Program fidelity	Percent of enrolled participants who received each of the following: 1) primary workshops, 2) employment supports, 3) substantive service contacts, 4) referrals Number of substantive service contacts and referrals per participant	nFORM MIS	
Dosage	Number of primary workshop hours received, percent of target hours received Subgroup exploratory analysis of how dosage varies by workshop and participant characteristics	nFORM MIS	

Co-parenting Relationships	Composite measure that takes the average of 5 survey items related to positive co-parenting interactions with the mother of participant's youngest child (continuous, scale from 1-5 where 1 is strongly disagree and 5 is strongly agree). Improvement will be measured by a participant's change score, calculated by subtracting their pre-program composite score from their post-program composite score.	nFORM Community-Based Fathers Survey (A13: d-h)	Reliability and validity will be assessed with a correlation matrix and factor analysis
Parenting Relationships	Daily hours spent with youngest child in past 30 days (change score from preprogram to post-program) Frequency of reaching out to youngest child in past 30 days (change score from preprogram to post-program) Composite measure that takes the average of 10-11 survey items related to positive parenting behaviors with youngest child (continuous, scale from 1-5 where 1 is Never, 2 is 1 to 2 days per month, 3 is 3 or 4 days per month, 4 is 2 or 3 days per week, and 5 is every day or almost every day). Improvement will be measured by a participant's change score, calculated by subtracting their pre-program composite score from their post-program composite score.	nFORM Community-Based Fathers Survey (A2b, A2c, A5a-d: a-k)	Reliability and validity will be assessed with a correlation matrix and factor analysis

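### As written, the R2 hours-with-child measure in effect keeps only fathers in contact at both surveys, so gained or lost contact carries no weight in it

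*SAP*

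**What the plan says.** All SAP references are to section 1, Data Analysis.

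- **Sample and range (measure definition matrix).** The row for hours per day with the youngest child has the sample "Has at least one child age 24 or younger, saw child within past month" and a range of 1 to 24. It names no survey for the contact condition.
- **Change score (Defining analysis measures).** "For standalone survey items, a change score will be calculated between a" participant's entrance and exit answers.
- **Missing data (Handling missing data, Outcomes).** For single items, "participants who do not respond to the item on either the pre- or post-survey will be excluded from the analytic sample" for that outcome. The same section rules out imputing truly missing outcome values.
- **Composite rule (same section).** "Participants who have not seen their child within the past month will have their parenting behavior responses set to" Never (1), and they stay in the sample for that outcome. No matching rule is given for hours.
- **Sample variation (Identify study sample).** "The analytic sample for particular outcome measures will vary based on missing data".
- **Non-response (Assessing non-response bias).** "We will conduct response rate analysis for each primary outcome of interest to assess non-response bias". The four groups to be compared are defined by which surveys were taken. The last is "respondents who completed both the pre-and post-survey (complete case").

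Protocol sections 1.1 and 1.2 make R2 a primary, confirmatory question about participants. Hours is one of three R2 measures in Protocol section 9.1. The others are frequency of reaching out and the behavior composite.

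**The concern.** A change in hours needs a value at both surveys. A father with no contact in the month before one survey has no admissible value there, because the range starts at 1 and nothing is imputed. He drops out of the analysis, even though his time with the child may have changed more than anyone's.

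Two things follow for this measure. A father who regains or loses contact during the program does not count. And membership of the sample depends partly on contact at exit, a state the program might itself affect. The Protocol's Program Summary describes a population of fathers with obstacles to involvement with their children, so changes in contact are plausible.

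At stake is what a paired t-test on hours can say. R2 asks about participants, but this result would describe time spent among fathers with contact at both ends.

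**Working it through.** The documents give no contact rate, mean, SD or expected change for this outcome, so there is no planned figure to reproduce. The check is one of logic, followed by a short illustration.

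**Step 1. Apply the rules to each contact pattern.**

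| Contact in past month | Entrance value | Exit value | Change score |
|---|---|---|---|
| Both surveys | 1 to 24 | 1 to 24 | Yes |
| Gained (exit only) | none | 1 to 24 | No |
| Lost (entrance only) | 1 to 24 | none | No |
| Neither | none | none | No |

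**Step 2. Vary the unstated timing of the contact condition.**

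- Judged at entrance: admits the both and lost patterns.
- Judged at exit: admits both and gained.
- Judged at both surveys: admits both only.
- Judged at either survey: admits both, gained and lost.

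Once a change score is required, each reading leaves only the first row. Reading the single-item rule as excluding only fathers who miss both surveys makes no difference, because a change score still needs two values.

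The one open link is the questionnaire. If it let a father without contact enter a number, the first, second and fourth readings could retain some such fathers. An entry of 0 would still lie outside the stated range. Hence the wording *in effect*.

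**Step 3. Compare with the composite.** A father who gains contact enters the composite at 1 and can rise, so his change counts. In the hours measure he is absent.

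**Step 4. Follow an excluded father through the response analysis.** If he completed both surveys he belongs to the complete-case group, with or without an hours score. The SAP promises the analysis per outcome, but its groups do not separate him. Whether he would be shown is unclear.

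**Step 5. Illustrate the size.** Every input here is an assumption. Let *p* be the share in contact at both surveys and *d* their mean change. Let *g* and *l* be the shares gaining and losing contact, and *H* the mean daily hours of those fathers when in contact, taken as 1 to 9. With no contact scored as 0:

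- result under the written rules = *d*
- all-father mean change = *p* × *d* + (*g* − *l*) × *H*

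With *d* = 0 and a net 5-point gain in contact, the all-father change is 0.05 × 1 = 0.05 to 0.05 × 9 = 0.45 hours per day. A net 5-point loss gives the same values with a minus sign. The written measure shows 0 in both cases.

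With *p* = 0.80 and *d* = 0.25, the written measure shows +0.25. The all-father change is:

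- no net change in contact: 0.80 × 0.25 = +0.20
- net 5-point gain: 0.20 + 0.05 = +0.25 (*H* = 1, no difference) to 0.20 + 0.45 = +0.65 (*H* = 9)
- net 5-point loss: 0.20 − 0.05 = +0.15 (*H* = 1) to 0.20 − 0.45 = −0.25 (*H* = 9)

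The gap can therefore be nil, positive or negative. The documents do not indicate which applies.

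**The case against.** The strongest reply is that this is a legitimate choice of estimand, stated in the plan. Hours among fathers who see the child is a coherent quantity. Never is an existing response on the composite's frequency scale, whereas the hours item asks about usual time per day. A zero would mix access with time spent. Restricted samples are also normal in this plan: co-parenting requires a child aged 24 or younger, and the account outcomes in Protocol section 9.1 apply only to those who entered without an account.

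Much of this stands. The conditional measure is valid and need not be replaced. But the account restriction is fixed at entry, whereas this one in effect also depends on contact at exit.

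Four stronger readings are tempting, and the documents do not support them.

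- *The restriction is hidden.* It is not. The Sample cell states the contact condition; only its timing is missing.
- *The Protocol conflicts with the SAP.* Protocol section 9.1 lists "Daily hours spent with youngest child in past 30 days (change score from preprogram to post-program") with no contact condition. But that table has no sample column and omits the child-age limit too. It is less detailed, not contradictory.
- *R2 ignores contact.* The composite registers it.
- *The hours result will be biased in a known direction.* No contact rates are given, so neither size nor direction can be claimed.

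The SAP does promise a response analysis for each primary outcome. The gap there is one of clarity, not of omission.

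**Conclusion.** The point holds for this one measure. Under the written rules, the hours outcome in effect estimates change among fathers in contact at both surveys. Gained or lost contact has no weight, and selection depends partly on a post-program state. This rests on the stated range, the need for two values, the exclusion rule and the absence of imputation. It also assumes that the questionnaire yields no usable hours value for a father without contact.

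The size is unknown. The 0.05 to 0.45 hours per day for a net 5-point shift in contact only shows scale under assumed hours of 1 to 9; it is not an estimate for this study. The conditional result is sound for what it measures. It cannot by itself carry a conclusion about all participants' hours under R2. The matter should be settled in the SAP before analysis, and it is cheap to do so.

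**What to change.** 1. State the survey or surveys at which past-month contact is judged.
2. Describe the existing result as change in hours among fathers in contact at both surveys.
3. Beside it, report an analysis of all fathers with a child aged 24 or younger who completed both surveys. Score reported no contact in the past month as 0 hours at the survey where it applies (range 0 to 24). Leave hours missing if the contact question was not answered.
4. Tabulate the numbers of fathers in contact at both surveys, gaining contact, losing contact, and with no contact at either.
5. State that the response analysis for this outcome covers fathers who completed both surveys but have no hours score.
6. Do not draw a participant-wide R2 conclusion on hours from the conditional result alone.

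The cost is SAP wording, one recode and a small table. No new data are needed, because the SAP already uses past-month contact to score the composite. The downside is that the supplementary measure is more skewed and mixes access with time spent, which is why the conditional result stays beside it.
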